9.3.2 Placebo Stimulation Device

The placebo devices will use a stimulation frequency of 10 Hz, a stimulation pulse width of 100 μ s and a stimulation current of 10mA. The stimulation ratio will be set to 0.8 for all subjects. All other parameters will be set according to the active stimulation device.

9.4 Number of Study Devices

Four stimulation timing controllers (manufactured by Liberate Medical, LLC) will be used for the study. Two devices will be used for the active stimulation group and two devices will be used for the placebo stimulation group. This will allow one operational device and one back up device per treatment group

Four Empi Continuum stimulators will be used for the study. Two devices will be set to deliver active stimulation and two devices will be set to deliver placebo stimulation. This will allow one operational device and one back up device per treatment group. The Empi Continuum is an FDA cleared stimulator for multiple patient use.

Six sets of electrodes will be provided per participant enrolled in the study to enable a new set of electrodes to be used every week that a patient is enrolled in the study. The PALS Platinum electrodes are FDA cleared electrodes that can be used multiple times with a single patient. 132 sets of electrodes will be used in total.

One variable orifice pneumotachograph will be provided per patient enrolled in the study (26 provided in total). The Braebon variable orifice pneumotachographs are FDA cleared and can be used multiple times with a single patient.

9.5 Packaging and Labeling of the Study Devices

Placebo and active stimulators will be able to be distinguished using a colored sticker, placed on the bottom of the device, with the meaning of each color identifiable only to the research team.

9.6 Device Administration

In both of the study arms (active and placebo stimulation), stimulation will be administered for thirty minutes, twice per day, 5 days per week for the shorter of six weeks or until the patient is weaned from mechanical ventilation by one of the two trained study researchers.

9.6.1 Electrode Placement

Adhesive surface electrodes (Pals Platinum, Axelgard, CA) will be placed bilaterally over the posterolateral aspect of the abdominal wall as described by Lim et al.¹⁹ Specifically, one pair of electrodes will be placed from the midline, angled diagonally downward, 2 cm below and parallel to the costal margin, toward the anterior superior iliac spine on each side of the abdomen¹⁹. A second pair of electrodes (cathodes) will directed from the midaxillary line at the eighth thoracic vertebral body level obliquely down toward the posterior superior iliac spine.¹⁹ (The electrodes will be positioned symmetrically on both sides of the abdomen.)¹⁹

9.6.2 Device Setup

Complete instructions for use will be provided with each study device. In addition, each study researcher will be fully trained by the PI prior to the start of the study. Briefly the following steps will be taken to setup the device:

1. Place the electrodes on the participant's abdomen (described in Section 9.6.1)
2. Connect the electrodes to the stimulator.
3. Connect the variable orifice pneumotachograph to the patient's endotracheal tube.
4. Connect the pneumotachograph's pressure hoses to the stimulation timing controller.
5. Turn on the stimulation timing controller and verify that the timing settings are correct.

9.6.3 Stimulation Session

At the start of the session the study researcher will apply 0.5 second bursts of stimulation starting from stimulation current of 5 mA and progressing in increments of 5 mA for each side of the abdomen until the participant reports that the sensation of stimulation is painful or until a maximum amplitude of 60 mA is reached. This upper limit in stimulation amplitude was based on the maximum tolerated stimulation amplitude found in our preliminary studies. A behavioral pain scale > 4 will be used to determine painful stimulation in patients who are unable to verbally communicate.¹⁸ The researcher will set the stimulation current to 90% of this maximum tolerable level (deemed acceptable in previous clinical studies performed by Liberate) and begin the session by turning on the exhalation synchronized stimulation mode of VentFree.

Throughout the session, heart rate, blood pressure, oxygen saturation and skin irritation will continuously be monitored. Every ten minutes, participants will be asked whether the intensity of abdominal wall muscle stimulation can be increased or should be decreased. During these 10-minute intervals, the investigator will quantify pain using the behavioral pain scale. If signs of distress develop, the investigator will stop the session and the attending physicians will provide immediate medical treatment, as appropriate. Criteria for distress include: a mean arterial blood pressure < 60 mmHg or > 110 mm Hg, heart rate < 40 beats per minute or > 130 beats per minute; respiratory rate > 40 breaths per minute, SpO₂ < 90%, score of > 4 on behavioral pain scale¹⁸, agitation or patient request to stop.

9.7 Device Deficiency/Failure

A log will be kept by the research team of any device deficiencies or failures. Such events will be discussed with the sponsor and, where appropriate, a defective device will be repaired and or replaced.

10 Apparatus

The specific apparatus that will be used for the study is described below.

10.1 Mouth Pressure Meter

MIP and MEP will be assessed using a hand-held respiratory pressure meter (MicroRPM, CareFusion, USA or similar). A disposable antimicrobial air filter will be used for each patient at each assessment session.

10.2 Peak Expiratory Flow Meter

PEF will be assessed using a hand-held mechanical peak flow meter. Each patient will be assigned an individual meter. The meter will be disinfected between uses.

11 Study Procedures

11.1 Concomitant Medications

Dose, route, unit frequency of administration, and indication for administration and dates of medication will be captured during the Baseline Visit, Intermediate Visit and Final Visit. No medications will be restricted as part of this study.

11.2 Demographics

Demographic information (date of birth, gender, race) will be recorded during the Baseline Visit.

11.3 Medical History

Relevant medical history, including history of current disease, other pertinent respiratory history, and information regarding underlying diseases will be recorded during the Baseline Visit.

11.4 Physical Examination

A complete physical examination will be performed at the Baseline Visit.

11.5 Vital Signs

Body temperature, blood pressure, pulse and respiratory rate will be recorded after resting for 5 minutes at the Baseline Visit, Intermediate Visit, and Final Visit.

11.6 Oximetry

Oximetry will be measured on fraction of inspired oxygen set by the treating physician with the participant at rest at the Baseline Visit, Intermediate Visit, and Final Visit.

11.7 Acute Physiology and Chronic Health Evaluation

The Acute Physiology and Chronic Health Evaluation II (APACHE II) score will be calculated by a study investigator at the Baseline Visit.

11.8 Expiratory Flow Limitation

The presence of expiratory flow limitation will be evaluated at the Baseline Visit using manual compression of the abdominal wall as described by Ninane et al.²⁰ During this maneuver, subjects will be asked to breathe through the VentFree pneumotachograph while the device is in expiratory flow limitation mode. The gentle manual compressions of the abdomen tests will be performed when subjects show regular breathing. For this purpose, the investigator will put one hand gently on the abdominal wall of the subject with the palm on the umbilicus oriented perpendicular to the axis between the xiphoid process and the pubis. Gentle palpation of the abdomen during two or three breathing cycles will easily allow recognition of the expiratory phase. The investigator will then inform the subject that he/she was soon going to push

on the abdominal wall. The gentle compression will be maintained throughout expiration and afterwards the investigator will remove his/her hand. If expiratory flow limitation is present, the gentle manual compressions of the abdomen will not increase expiratory flow either during the whole tidal exhalation or during part of it. On the other hand, if expiratory flow is absent, the gentle manual compressions of the abdomen will increase expiratory flow during exhalation. Gentle manual compressions of the abdomen are known to be well tolerated without untoward effects.

11.9 Maximum Expiratory Pressure and Maximum Inspiratory Pressure

Maximum Expiratory Pressure (MEP) and Maximum Inspiratory Pressure (MIP) will be measured at the Baseline Visit, Intermediate Visit, and Final Visit using a cuff inflated cannula as described by Vitacca et al.²¹

11.10 Thickness of the Abdominal Wall Muscles

The end inspiratory and the end expiratory thickness of the external oblique, internal oblique and transversus abdominis muscles will be measured using ultrasound²² at the Baseline Visit, Intermediate Visit and Final Visit.

11.11 Thickness of the Diaphragm

The end inspiratory and the end expiratory thickness of the diaphragm will be measured using ultrasound²² at the Baseline Visit, Intermediate Visit and Final Visit.

11.12 Cough Peak Flow

CPF will be measured at the Baseline Visit, Intermediate Visit, and Final Visit through a deflated cuff as described by Winck et al.²³

11.13 Sensation of Stimulation

The participant's sensation of stimulation will be measured using the behavioral pain scale every five minutes while receiving electrical muscle stimulation.

11.14 Adverse Events

Information regarding occurrence of adverse events will be captured throughout the study. Duration (start and stop dates and times), severity/grade, outcome, treatment and relation to study device will be recorded on the case report form (CRF).

11.15 Measures of Treatment Compliance

The study treatment devices will automatically record the date, time and duration of stimulation for an individual patient to a memory card.

12 Study Schedule

A Schedule of Events representing the required testing procedures to be performed for the duration of the study is diagrammed in Appendix 1. A description of each procedure is provided in Section 11

Prior to conducting any study-related activities, written informed consent and the Health Insurance Portability and Accountability Act (HIPAA) authorization must be signed and dated by the participant.

12.1 Baseline Visit - Day 1

On day 1 the investigators will review the study with the participant and obtain written informed consent and HIPAA authorization. After consent has been obtained they will record the patient's demographic data, medical history and concomitant medications.

The investigators will determine if the patient meets the study inclusion and exclusion criteria. If the patient does not meet the criteria then no further procedures will be performed and they will be withdrawn from the study. If the patient does meet the criteria then the investigator will randomize the patient to a treatment group.

The study researcher will record their vital signs, oximetry, expiratory flow limitation, APACHE II score, MIP, MEP, thickness of the abdominal wall muscles and diaphragm, CPF and resting breathing parameters.

12.2 Stimulation Visits – Days 2 - 22

Patients will participate in Stimulation Visits two 2 per day in 5 days every week. Specifically, patients will participate in morning and afternoon Stimulation Visits 5 times between days 2 and 8, 5 times between days 9 and 15 and 5 times between days 15 and 22.

The investigators will administer sixty minutes of stimulation to the participant as described in Section 9.6. In addition, the investigators will record adverse events related to stimulation or otherwise.

12.3 Intermediate Visit – Day 23

The Intermediate Visit will ideally take place on day 21. However, if necessary the Intermediate Visit may be conducted no earlier than day 20 and no later than day 25, providing that it occurs after 15 Stimulation Visits.

At the start of the visit the investigators will measure MEP, MIP, CPF, thickness of the abdominal wall muscles and diaphragm, resting breathing parameters, changes to medications and adverse events related to stimulation or otherwise.

12.4 Stimulation Visits – Days 24 – 44

Patients will participate in a Stimulation Visits 2 times per day in 5 days every week. Specifically, patients will participate in morning and afternoon Stimulation Visits 5 times between days 24 and 30, 5 times between days 31 and 37 and 5 times between days 38 and 44.

The stimulation session will then continue as described in Section 9.6. In addition, the investigators will record adverse events related to stimulation or otherwise.

12.5 Final Visit – Day 45

The Final Visit will ideally take place on day 45. However, if necessary the Final Visit may be moved no earlier than day 43, providing that it occurs 15 Stimulation Visits after the Intermediate Visit, and no later than day 47.

During this visit the investigators will record the participant's MEP, MIP, thickness of the abdominal wall muscles and diaphragm, CPF, resting breathing parameters and adverse events related to stimulation or otherwise.

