A small number of adverse events were reported in the literature. These were minor, infrequent and transient in nature. No adverse events have been reported in Liberate Medical clinical studies conducted to date. The FDA MAUDE database included reports of injuries and malfunctions resulting from electrical stimulation devices. The reported adverse events were minor in nature, and no further complications were reported. Based on the available safety information, AFES offers an acceptable safety profile.

The combined results from the prospective clinical trials conducted by Liberate Medical and the literature included in the structured literature review have demonstrated that abdominal stimulation applied in synchrony with exhalation can be used to acutely improve breathing volumes in a range of different patient groups. In addition the studies cited in the literature review indicate that abdominal muscle training using electrical stimulation can be used to improve unassisted respiratory function in SCI and that this improvement is sustained after the cessation of stimulation training. Finally, two studies indicate that abdominal stimulation may be able to be used to assist ventilator weaning. However, additional studies are required to verify the abdominal muscle training results in additional patient groups and to determine the functional benefit of abdominal stimulation for patients.

5 Objectives of the Clinical Investigation

The primary objective of this study is to determine whether NMES applied to the abdominal wall muscles in synchrony with exhalation can increase the strength of the respiratory muscles in prolonged mechanical ventilation patients. If feasible it will be used to design a follow up trial on clinically relevant endpoints.

The secondary objectives of the study is to evaluate whether this intervention also affects: (1) the thickness of the abdominal wall muscles and the diaphragm, (2) functional respiratory measurements, and (3) weaning outcome.

6 Study Design

This is a single center, participant blinded randomized placebo-controlled pilot trial that includes 12 patients in the intervention arm and 12 patients in the placebo arm.

Screening data will be reviewed to determine participant eligibility. Patients who meet all of the inclusion criteria and none of the exclusion criteria and who are willing to participate in the study will be entered into the investigation.

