9.2 Blinding

The difference between active and placebo stimulation can be distinguished visually as active stimulation causes a tetanic muscle contraction whereas placebo stimulation causes a sub-tetanic muscle contraction. Therefore study personnel who apply the treatment to subject will not be blinded to study patients' treatment group assignment.

The following procedures will be used to ensure that patients are blinded to the treatment group that they have been assigned to:

- Study personnel will be instructed not to inform patients as to whether a tetanic or twitch contraction is the active or placebo treatment arm of the study.
- The appearance of the active and placebo stimulation devices will be identical.

In addition, all clinical staff not involved in the study and all study personnel who do not apply stimulation to patients will be blinded to the treatment group assignment of participants. This measure will help ensure that decisions to attempt weaning are unrelated to the study and are only based on clinical care.

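### Nothing in the protocol requires baseline MIP and MEP to be recorded before allocation is revealed, so the primary outcome's baseline can be taken with allocation known

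*Combined protocol and SAP*

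**What the plan says.** Section 12.1 sets out the Baseline Visit as consent, then demographics, history and medications, then the check of eligibility. It continues: "If the patient does meet the criteria then the investigator will randomize the patient to a treatment group". A separate paragraph follows: "The study researcher will record their vital signs, oximetry, expiratory flow limitation, APACHE II score, MIP, MEP, thickness of the abdominal wall muscles and diaphragm", with cough peak flow and resting breathing completing the list.

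The study researcher is also the person who treats. Section 9.6 has stimulation given "until the patient is weaned from mechanical ventilation by one of the two trained study researchers", and Section 9.6.3 has the study researcher set the current at each session. On masking, Section 9.2 says: "Therefore study personnel who apply the treatment to subject will not be blinded to study patients' treatment group assignment". It adds that "all study personnel who do not apply stimulation to patients will be blinded to the treatment group assignment of participants". Section 6 labels the design: "This is a single center, participant blinded randomized placebo-controlled pilot trial".

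MIP and MEP are the primary outcome (Section 7.1), measured at the Baseline, Intermediate and Final Visits (Section 11.9). Section 9.1 describes a computer-generated 1:1 sequence and no step that withholds the allocation until baseline testing is done.

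**The concern.** MIP and MEP are maximum-pressure tests, and patients who cannot follow verbal instructions are excluded (Section 8.3). That fits a measurement that depends on effort and coaching, although the documents do not use those terms. An assessor who knows the arm could, without intending to, coach one group differently or accept a different best effort.

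When this happens at baseline, the error enters every estimate that uses the baseline. A baseline recorded too low in the active arm makes a later value look like improvement, and one recorded too high hides improvement. Randomisation gives no protection, because the distortion arises after it. With about 12 participants per arm, the data could not separate such a shift from chance imbalance.

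**Working it through.** The plan states no figure on this point: no SD, no correlation between baseline and follow-up, and no expected effect. The check is therefore a reading of the text, followed by an illustration on assumed values.

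**Reading of the text**

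1. *Order.* In Section 12.1 randomisation directly follows eligibility, and the measurements are in the next paragraph. The consent and eligibility steps are linked by time words. The measurement paragraph is not.
2. *Who measures.* The study researcher (Section 12.1).
3. *Who treats.* The study researcher, a role held by two people (Section 9.6).
4. *Masking.* Staff who apply stimulation are unblinded. Other study personnel are blinded (Section 9.2), but no passage assigns MIP and MEP to them.
5. *Safeguard.* No section requires baseline MIP and MEP to precede randomisation, or holds back the allocation until they are recorded.

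A site that follows Section 12.1 in the order printed is compliant, and its assessor may know the arm.

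**Size, by type of analysis**

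Assumptions, none taken from the documents: no true effect; recorded baseline lower by b SD in one arm; equal SDs at baseline and follow-up; correlation r between them.

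- Change from baseline: bias = b. For b = 0.2 to 0.3, the bias is 0.2 to 0.3 SD.
- Baseline-adjusted model: bias ≈ r × b.
  - 0.2 × 0.5 = 0.10
  - 0.2 × 0.7 = 0.14
  - 0.3 × 0.5 = 0.15
  - 0.3 × 0.7 = 0.21
- Final values only: bias = 0, because the baseline is not used.

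A simulation with wider assumptions (12 per arm, 4,000 replicates, two-sided 5% level) gave the same pattern:

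| r | b (SD) | Change: bias (SD), false-positive rate | Adjusted: bias (SD), false-positive rate | Final only: false-positive rate |
|---|---|---|---|---|
| 0.5 | 0.25 | 0.255, 8.6% | 0.127, 6.0% | 4.4% |
| 0.5 | 0.50 | 0.494, 20.3% | 0.247, 9.8% | 5.2% |
| 0.8 | 0.25 | 0.250, 14.6% | 0.198, 11.6% | 5.2% |
| 0.8 | 0.50 | 0.498, 44.8% | 0.399, 31.0% | 4.5% |

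**Which row applies**

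Section 17 names t-tests, non-parametric alternatives, and crude and adjusted regression. It does not say whether MIP and MEP enter as change, with baseline as a covariate, or as final values. Section 17.1 describes the primary outcome as an effect on strength over the course of the study, which suggests that baseline matters but does not settle it.

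**The case against.** The strongest reply is that the order is inferred. The measurement paragraph could simply list what one role does on Day 1. It includes vital signs and oximetry, yet eligibility turns on oxygen saturation and temperature (Section 8.2). Either those readings come before randomisation and the paragraph is not chronological, or eligibility uses separate screening data (Section 6). This stands: the text does not prove that MIP and MEP come after randomisation. It does not place them before it either.

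Second, Section 12.1 has the investigator randomise and the study researcher measure, and stimulation begins only on Day 2. The researcher might not yet know the arm. Role terms are also loose: Section 12.2 has the investigators giving stimulation, where Section 9.6 names study researchers. This also stands, so knowledge of the arm on Day 1 is a possibility and not a stated fact.

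A reader might infer more in three ways, none of which the documents support:

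- *That Appendix A confirms the order.* It lists randomisation above MIP and MEP, but also above medical history, which Section 12.1 takes earlier. Its rows are not a timeline.
- *That the primary result will be biased.* With a comparison of final values the baseline plays no part, and the size of any shift is hypothetical.
- *That participants will be lost after randomisation because they cannot do the baseline tests.* Patients unable to follow verbal instructions are excluded beforehand, and the documents give no rate of failed tests.

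**Conclusion.** The point holds as a possibility that the plan leaves open. On no reading does the text protect the baseline MIP and MEP from known allocation, and the order as printed permits it. That the assessor will know the arm, and that the baseline will shift, are not established.

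Under the assumed shift of 0.2 to 0.3 SD, the bias runs from zero (final values only), through about 0.10 to 0.21 SD (baseline-adjusted, r from 0.5 to 0.7, equal SDs), to 0.2 to 0.3 SD (change score). These figures show direction and scale only. The point is worth acting on because it concerns the primary outcome and the remedy costs almost nothing.

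**What to change.** In Section 12.1, move the randomisation sentence to after the paragraph of baseline measurements. Add a sentence stating that all baseline tests are completed and entered on the CRF before the allocation is revealed to anyone who performs them.

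Because stimulation starts on Day 2, this adds no visit, procedure or participant. The one small downside is that baseline tests are carried out before randomisation is confirmed.

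The change protects the baseline only. The Intermediate and Final MIP and MEP are taken by the investigators (Sections 12.3 and 12.5) with no stated masking of the assessor, and reordering Day 1 does not remove that possible exposure. Naming an assessor who does not apply stimulation for MIP and MEP at every visit would address it, but is a separate change that needs suitable staff.
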